## Statistical Analysis Plan (RotW)

Final v1.0, 08FEB2022

SG018

The above sensitivity analyses represent a change to the handling of the intercurrent event 'Withdrawal from study' to a treatment policy.

A third sensitivity analysis will be performed on the subset of patients who have completed Day 35 or who have died prior to Day 35. Patients who did not withdraw prior to Day 35 and who have at least 1 completed assessment between Day 31 and Day 35 will be considered completers. This is to exclude patients who are lost to follow-up during the first 35 days of the study but are re-contacted at a later date. The key secondary analysis model will be repeated for this subset.

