8.1 Sample Size Determination

Success will be determined if at least one of the primary endpoints is declared statistically significant by the primary analysis. A sample size of 610 patients in total using a 1:1 randomisation ratio (305 patients per treatment arm) has been chosen to provide at least 90% power to detect a hazard ratio of 1.45 in time to hospital discharge and a hazard ratio of 1.7 in time to recovery and at least 95% power to declare statistical significance on at least one of the primary endpoints. This sample size has been calculated using a global 2-sided alpha level of 0.05 and adjusting for the Hochberg procedure to allow for multiple comparisons. This also allows for an interim analysis to assess futility after the first 300 randomised patients have completed the Day 35 visit or have withdrawn from the study.

The sample size calculation assumes a hospital discharge rate in the placebo treatment arm of 70% at Day 28, a recovery rate in the placebo treatment arm of 30% at Day 28 and a dropout rate of 25% over the 28-day evaluation period with time to dropout exponentially distributed.

By their definition the two primary endpoints are naturally correlated. This correlation has been estimated from prior study data and has also been considered in the sample size calculation.

More details regarding the sample size calculation used for the study will be provided in the SAP.

The key secondary endpoint of progression to severe disease or death within the 35-day study period will be formally tested, provided statistical significance is declared in both of the primary endpoints.

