## 6 Sample Size

A sample size of 610 subjects in total using a 1:1 randomisation ratio (305 subjects per treatment arm) has been chosen to provide at least 90% power to detect a hazard ratio of 1.45 in time to hospital discharge and a hazard ratio of 1.7 in time to recovery and at least 95% power to declare statistical significance on at least one of the primary endpoints. This sample size has been calculated using a global 2-sided alpha level of 0.05 and adjusting for the Hochberg procedure to allow for multiple comparisons. This sample size also allows for an interim analysis to assess futility after the first 300 randomised subjects (150 subjects per treatment arm) have completed the Day 35 assessment or have withdrawn from the study. The futility analysis is planned to be non-binding.

The power of the study was confirmed via simulation as follows:

Time to recovery and time to discharge in the placebo subjects were drawn from exponential distributions with rate parameters:

$$\text{Placebo Time to Sustained Recovery} \sim \text{Exp}\left(\frac{\log\left(\frac{100}{70}\right)}{28}\right) \text{ and}$$

$$\text{Placebo Time to Sustained Discharge} \sim \text{Exp}\left(\frac{\log\left(\frac{100}{30}\right)}{28}\right)$$

In the simulations, this gives the placebo arm:

- a median time to recovery (50% recovery) of approximately 54.4 days and a 30% recovery at exactly 28 days

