## Statistical Analysis Plan (RotW)

Final v1.0, 08FEB2022

SG018

- a median time to discharge (50% discharge) of approximately 16.1 days and a 70% discharge at exactly 28 days

Assumed hazard ratios (SNG vs Placebo) for recovery and discharge of 1.35 and 1.7 respectively, this data can be simulated:

$$\text{Active Time to Sustained Recovery} \sim \text{Exp}\left(\frac{\log\left(\frac{100}{70}\right)}{28 * 1.35}\right) \text{ and}$$

$$\text{Active Time to Sustained Discharge} \sim \text{Exp}\left(\frac{\log\left(\frac{100}{30}\right)}{28 * 1.7}\right)$$

This gives the active arm:

- a median time to recovery (50% recovery) of approximately 40.3 days and a 30% recovery at approximately 21.5 days
- a median time to discharge (50% discharge) of approximately 9.5 days and a 70% discharge at approximately 16.5 days

It was additionally assumed that study withdrawal followed an exponential distribution on both treatment arms

$$\text{Withdrawal From Study} \sim \min\left(\text{Exp}\left(\frac{\log\left(\frac{100}{75}\right)}{28}\right), 28\right)$$

so that in the simulations, on average 25% of patients withdraw early from the study (i.e. before Day 35), and the other 75% have complete follow-up.

All patients were assumed to contribute to the primary endpoints up to their withdrawal from the study, thus patients who withdrew may still meet one or both primary endpoints. Patients who withdrew early without meeting the primary endpoint(s) were censored in the simulation analyses. All patients were administratively censored at the last time point (on Day 28).

An interim analysis at which both primary endpoints were assessed was simulated using the data from the first 300 randomised subjects (150 on each treatment arm). The simulated study was stopped for futility if the Z statistic (calculated as the partial likelihood log hazard ratio for SNG vs Placebo divided by its standard error) for both primary analyses was less than 1.4. Otherwise the simulated study continued to recruit the remaining 310 subjects (155 on each treatment arm) and the pooled (pre-interim and post-interim) simulated data was analysed at the final analysis.

The power of the overall study to meet both primary endpoints was simulated as over 90%. The power to meet at least one primary endpoint was approximately 95%.

In the case of the complete absence of efficacy in one of the primary endpoints the power to meet the other primary endpoint was approximately 85%.

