**9.2.3.3 Sensitivity Analyses of the Key Secondary Estimand**

The sensitivity to missing data will be assessed in the same way as described for progression to severe disease or death in [Section 9.2.1.3](#).

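### The third key-secondary sensitivity analysis selects patients on outcome: recorded deaths are always kept, but withdrawn survivors and withdrawn patients with known non-fatal progression are dropped

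*SAP*

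**What the plan says.** SAP 9.2.1.3 lists three sensitivity analyses for withdrawal before progression to severe disease or death: a tipping-point imputation, a jump-to-reference imputation, and a third analysis "performed on the subset of patients who have completed Day 35 or who have died prior to Day 35". Completers are defined as "Patients who did not withdraw prior to Day 35 and who have at least 1 completed assessment between Day 31 and Day 35". The stated aim of that definition is to leave out patients who were lost to follow-up and reached again later. The key secondary model is then refitted on the subset.

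SAP 9.2.2.3 (intubation or death) and 9.2.3.3 (death) adopt the same set of analyses: "The sensitivity to missing data will be assessed in the same way as described for progression to severe disease or death".

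The main key secondary analysis uses the ITT population with a while-on-study policy (SAP 7.3.1.3 and Table 14). A score of 5 or more at any post-baseline assessment up to Day 35 is an event (SAP 5.3.1.3), so progression seen before withdrawal counts. Deaths after withdrawal count only if consent allows them to be recorded (Table 20).

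Protocol 8.4.2 names different subsets: Day 28 completers, and patients who withdrew before Day 35. SAP Section 15 does not list the change.

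**The concern.** Membership of the subset depends on the outcome. A patient who dies on Day 8 had only eight days in which to withdraw and is kept. A survivor had 35 days in which to withdraw and is lost by withdrawing on any of them. Even if withdrawal has nothing to do with prognosis, deaths are therefore retained more often than survivors.

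The rule also deletes known endpoints. A patient ventilated on Day 6 who withdraws on Day 20, or who has no score on Days 31-35, is an event in the main analysis. No endpoint information is missing for that patient, yet an analysis of missing data removes them. As a result, the fatal and non-fatal parts of each composite endpoint are retained at different rates.

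The key secondary estimand is a difference in probabilities, which is the scale that this selection distorts. A gap between the main and subset risk differences could be read as sensitivity to withdrawal when the selection rule alone would produce one.

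**Working it through.** **Inputs from the documents.** Withdrawal is exponential with rate ln(100/75)/28 in both arms, with 305 patients per arm (SAP 6). The Protocol (8.1) states "a dropout rate of 25% over the 28-day evaluation period with time to dropout exponentially distributed". The SAP text says "on average 25% of patients withdraw early from the study (i.e. before Day 35), and the other 75% have complete follow-up". Both readings are worked below.

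**Assumptions.** The documents give no death or progression rates. I assume 35-day death risks of 10% v 5%, deaths spread evenly over T days, and withdrawal that is independent and equal in both arms.

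**The plan's own figure.** 1 - exp(-28 × ln(100/75)/28) = 25.0%, as stated. The same rate carried on to Day 35 gives 1 - 0.75^(35/28) = 30.2%.

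**Death: retention.** With withdrawal rate c, survivors are kept with probability s = exp(-35c), and deaths with r = (1 - exp(-cT))/(cT). The subset risk is pr / (pr + (1 - p)s).

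| Reading | T (days) | s | r | Subset risks | Difference | Excess over 5.0 points |
|---|---|---|---|---|---|---|
| 25% by Day 35 | 35 | 0.750 | 0.869 | 11.4% v 5.7% | 5.7 points | +13% |
| 25% by Day 28 | 35 | 0.698 | 0.840 | 11.8% v 6.0% | 5.8 points | +17% |
| 25% by Day 28 | 21 | 0.698 | 0.899 | 12.5% v 6.4% | 6.2 points | +23% |
| 25% by Day 28 | 14 | 0.698 | 0.931 | 12.9% v 6.6% | 6.4 points | +27% |

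For the second row: 0.10 × 0.840 / (0.10 × 0.840 + 0.90 × 0.698) = 0.118. With 25% by Day 35, T = 21 and T = 14 give +18% and +21%.

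**Death: odds ratio.** The odds in each arm are multiplied by the same r/s, which cancels. The true value is (0.10/0.90)/(0.05/0.95) = 2.11, and the subset gives 2.11 in every row.

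**Main analysis in the same example (second row).** It reads 8.4% v 4.2%, a difference of 4.2 points. The two analyses therefore show 4.2 and 5.8 around a true 5.0, with no informative withdrawal at all.

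**When the direction changes.** In one arm of N patients, let D be recorded deaths, C completers, W withdrawn patients and q the later death risk of those withdrawn. The subset estimate is e = D/(D + C) and the true risk is (D + qW)/N. Since N = D + C + W, the bias is (W/N)(e - q). The subset overstates an arm's risk only if q < e. The next results assume constant hazards and 25% withdrawn by Day 35 unless stated, with risks of 10% (placebo) v 6%:

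- Independent, equal withdrawal: subset difference -4.54 points, true -4.00.
- Later death hazard of withdrawn patients three times as high: placebo risk 11.4% against a true 12.3%; difference -4.54 against -4.85.
- Withdrawal 10% placebo, 40% SNG001: -2.79 against -4.00.
- No true effect (10% in both arms): zero bias with equal withdrawal; a false difference of 0.65 points with 25% v 15%.

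**Severe disease or death.** Assume a 20% true risk, progression on Days 1-10, death 1-20 days later in a fraction f of progressors, and 25% withdrawal by Day 28. Fatal progressors are kept with probability 0.850; non-fatal progressors and non-progressors with 0.698. For f = 0.5, events are kept at 0.5 × 0.850 + 0.5 × 0.698 = 0.774, so the subset reads 0.2 × 0.774 / (0.2 × 0.774 + 0.8 × 0.698) = 21.7%. For f = 0.4 to 0.6 the excess is 7-10%. Progression is observed before withdrawal with probability 0.945, so (0.945 - 0.774)/0.945 = 18% of observed progressions are discarded (about 16-20% over the range of f).

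That upward shift needs progressors to withdraw no faster than others. In a separate simulation (true 15%, half of progressors dying, 25% withdrawn by Day 35), the subset reads 15.5% when withdrawal is unrelated to progression, but 14.1% or 12.0% when progressors withdraw two or four times as fast.

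**The case against.** The strongest reply has four parts.

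1. **Relative measures survive.** The refitted logistic model also reports an odds ratio and p-value. For death, under independent and equal withdrawal, the odds ratio is preserved. In the 10% v 5% example the unadjusted z for the log odds ratio is 2.09 in both the subset and the main analysis. This stands. A reader might infer that the analysis cannot be interpreted at all; for the odds ratio for death that goes too far.

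2. **The direction is conditional.** A reader might infer that the subset always overstates death risk and the treatment difference. Neither the documents nor the arithmetic supports that. It needs the later risk of withdrawn patients to be below the subset estimate and, for the difference, a real effect and similar withdrawal in both arms. For the composites, losing non-fatal progressors pulls the estimate down. This stands and limits the claim.

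3. **Other analyses already cover the question.** The tipping-point imputation with delta = 1 is an all-ITT missing-at-random analysis that keeps observed progressions and adjusts for covariates. The rest of the grid and jump to reference address informative withdrawal. This limits the consequence, but does not repair the third analysis, which would still be reported beside them.

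4. **Keeping deaths has a purpose.** A pure Day 35 completer set would contain none. True, but that explains the rule without removing the imbalance, and it does not justify deleting patients whose progression was observed.

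**Conclusion.** The point holds as selection on outcome in one sensitivity analysis, applied to three endpoints. Under the plan's own withdrawal model (exponential, same distribution in both arms, taken as independent of prognosis), the subset inflates the Day 35 death risk and any non-zero risk difference: about +13% if 25% withdraw by Day 35 and about +17% if 25% withdraw by Day 28, with assumed death risks of 10% v 5% spread evenly over 35 days. Earlier deaths make it larger. The odds ratio for death is essentially unchanged. With informative or unequal withdrawal, and for the two composites, the direction cannot be stated in advance.

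The deletion of patients with known non-fatal progression follows from the SAP wording and needs no numerical assumption; only its extent does. The rule covers recorded deaths, not every death, because deaths after withdrawal enter only with consent.

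The formal key secondary tests, the tipping-point analysis and jump to reference are not affected. The change is worth making because the risk difference is the estimand and this analysis is there to show how far it depends on withdrawals.

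**What to change.** In SAP 9.2.1.3, and by reference in 9.2.2.3 and 9.2.3.3, replace the subset analysis with the Day 35 Kaplan-Meier risk difference in all ITT patients eligible for the endpoint, for time to first OSCI of 5 or more (6 or more; death). Count every event observed before withdrawal, and censor event-free patients at their last OSCI assessment. Each endpoint includes death, so there is no competing event. Under independent withdrawal this targets the true risk.

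If weighting is preferred, keep every patient whose endpoint was observed, and weight by the inverse probability of remaining uncensored to the earlier of the event and Day 35. Weighting only the existing completer set would still discard withdrawn progressors. Adding those patients back without weights would still favour events over non-events.

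Section 15 should also record the departure from the subsets in Protocol 8.4.2.

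The cost is SAP wording and a standard program on OSCI data already collected daily to Day 35. The simple Kaplan-Meier estimate is not covariate-adjusted, assumes independent censoring, and overlaps with the delta = 1 imputation. The tipping-point and jump-to-reference analyses should stay to cover informative withdrawal.

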#### 9.2.1.3.1 *Sensitivity to the Severe Disease Definition*

The following analyses will explore different subsets of the progressed population:

- A sensitivity analysis which will only consider OSCi assessments between Day 6 and Day 35 for the derivation of progression to severe disease or death. The purpose of this analysis is to assess the rate of progression after a sufficient period of time has passed for the study drug to have a beneficial effect. Patients who die prior to Day 6 will be excluded from the analysis.
- A sensitivity analysis which will exclude short term progressions. Short term progressions are defined by OSCi scores of  $\geq 5$  which are not maintained for consecutive scheduled assessments.
- A summary of patients with a maximum OSCi score of 5. This summary will assess patients who progress to non-invasive or high flow oxygen but who do not progress to intubation.
- A summary of patients who progress to severe disease but are subsequently discharged from hospital.
- A summary of patients who progress to severe disease but subsequently recover.

#### 9.2.1.4 *Supportive Estimands*

A supportive estimand for the key secondary endpoint will be defined as follows. The difference in probabilities for SNG001 versus placebo for progression to severe disease or death within 35 days of first dose will be estimated for the per protocol population. Reasons for excluding patients from the PP population are described in [Section 7.1.2](#). Of note, many of the reasons are based on assessments prior to randomisation and treatment and so the exclusions are independent of treatment. Intercurrent events will be handled as per table 15.

Table 15: Intercurrent events and policies for the supportive estimand of progression to severe disease or death

Intercurrent event	Policy
Death	Composite variable: The definition of severe disease includes patients who die within 35 days of first dose, regardless of their OSCi assessments.
Missed 2 of the first 3 scheduled doses	Hypothetical (estimand for a situation with treatment compliance): OSCi assessments will be considered missing if two doses or more of the randomised treatment were missed within the first three days of therapy, with the corresponding patients excluded from the PP analysis set. A single dose within the first three scheduled dosing days is not expected to be sufficient for the study drug to be effective, therefore this

## Statistical Analysis Plan (RotW)

Final v1.0, 08FEB2022

SG018

	approach will help establish the true treatment effect. It is assumed that such exclusions are not related to treatment.
Other premature treatment discontinuation and missed doses	Treatment policy: Severe disease will be determined regardless of treatment discontinuation and the number of missed doses (other than missing 2 out of the first 3 scheduled doses).
Withdrawal from study	While-on-study: Patients will only be considered having severe disease if observed and recorded whilst participating in the study. This assumes the treatment effect is independent to reason for study withdrawal.
Other protocol deviations affecting efficacy	Hypothetical (estimand for a situation with no protocol deviations affecting efficacy): To establish the true treatment effect all OSCI assessments will be considered missing if protocol deviations affecting efficacy are recorded on or prior to Day 35.
Medications affecting efficacy	Treatment policy: Severe disease will be determined regardless of any concomitant medication use.

A second supportive estimand will estimate the difference in probabilities for SNG001 versus placebo for progression to severe disease or death within 35 days of first dose in the per protocol population who do not receive medications affecting efficacy. Medications affecting efficacy will be defined as COVID-19 therapies which are approved for use (including emergency use) at the time of the primary analysis and will be handled as per table 16.

**Table 16: Intercurrent events and policies for the second supportive estimand of progression to severe disease or death**

Intercurrent event	Policy
Death	Composite variable: The definition of severe disease includes patients who die within 35 days of first dose, regardless of their OSCI assessments.
Missed 2 of the first 3 scheduled doses	Hypothetical (estimand for a situation with treatment compliance): OSCI assessments will be considered missing if two doses or more of the randomised treatment were missed within the first three days of therapy, with the corresponding patients excluded from the PP analysis set. A single dose within the first three scheduled dosing days is not expected to be sufficient for the study drug to be effective, therefore this approach will help establish the true treatment effect. It is assumed that such exclusions are not related to treatment.
Other premature treatment discontinuation and missed doses	Treatment policy: Severe disease will be determined regardless of treatment discontinuation and the number of missed doses (other than missing 2 out of the first 3 scheduled doses).

Withdrawal from study	While-on-study: Patients will only be considered having severe disease if observed and recorded whilst participating in the study. This assumes the treatment effect is independent to reason for study withdrawal.
Other protocol deviations and prior medications affecting efficacy	Hypothetical (estimand for a situation with no protocol deviations or prior medications affecting efficacy): To establish the true treatment effect all OSCI assessments will be considered missing if protocol deviations affecting efficacy are recorded on or prior to Day 35 or medications affecting efficacy are being received at the time of first dose.
Concomitant medications affecting efficacy	Composite: Only assessments prior to the first dose of any medication affecting efficacy will be considered for the derivation of severe disease.

#### 9.2.1.5 *Analysis of the Supportive Estimands*

The supportive estimand of progression to severe disease or death will be analysed using the same methods as the key secondary estimand, as detailed in [Section 9.2.1.2](#).

### 9.2.2 Progression to Intubation or Death

#### 9.2.2.1 *Key Secondary Estimand*

The key secondary estimand will be the difference in probabilities for SNG001 versus placebo for progression to intubation or death within 35 days of first dose of patients in the ITT population. Intercurrent events will be handled as per Table 17.

**Table 17: Intercurrent events and policies for the key secondary estimand of progression to intubation or death**

Intercurrent event	Policy
Death	Composite variable: The definition of the endpoint includes patients who die within 35 days of first dose, regardless of their OSCI assessments.
Premature treatment discontinuation and missed doses	Treatment policy: Intubation or death will be determined regardless of treatment discontinuation and the number of missed doses.
Withdrawal from study	While-on-study: Patients will only be considered to be intubated if observed and recorded whilst participating in the study. This assumes the treatment effect is independent to reason for study withdrawal.
Other protocol deviations and concomitant medications affecting efficacy	Treatment policy: Intubation or death will be determined regardless of any concomitant medication use or protocol deviations.

